3.2.3 PRISM Trial Flowchart

Figure 2 PRISM trial of progesterone in women with vaginal bleeding in early pregnancy

3.3 Randomisation

3.3.1 The Randomisation Process

Immediately after all eligibility criteria have been confirmed, consent has been obtained and all baseline prognostic factors gathered, a patient will be randomised into the trial. Participants will be randomised into the trial by a secure online randomisation system which is available via the MedSciNet Clinical Trial Framework. Each participating centre and each authorised member of the research team will be provided with a unique log-in username and password for this purpose. Online randomisation will be available 24 hours a day, seven days a week apart from short periods of scheduled maintenance. As a back-up, authorised members of the research team will be able to make one telephone call per participant to the toll-free randomisation service ([name]). Telephone randomisations will be available Monday to Friday, between 09:00 and 17:00.

Randomisation Notepads (a sample document is available separately) will be provided to investigators and may be used to collate the necessary information prior to randomisation. All the questions and data items on the Randomisation Notepad must be answered before a trial number and pack number may be given. If some data items are missing, randomisation will be suspended but may be resumed once the information is available. Only when all the eligibility criteria and baseline data items have been provided, will the trial and pack numbers be given and a confirmatory email sent to the randomising investigator, the local PI and the research midwife/nurse. The trial number will be linked to a treatment pack number that will be available in the local hospital pharmacy, and the pharmacy will also receive notification of the randomisation by email.

3.3.2 Randomisation Methods and Stratification Variables

Participants will be randomised online via a secure internet facility in a 1:1 ratio through an Integrated Trial Management System. A "minimisation" procedure using a computer-based algorithm will be used to avoid chance imbalances in important stratification variables. Strata used in the minimisation will be:

- Age (<35, ≥35 years).
- Body Mass Index (BMI) (<30, ≥30).
- Fetal heart activity (present, absent).
- Estimated gestation at presentation (<42, ≥42 days).
- · Amount of bleeding (PBAC [Pictorial Bleeding Assessment Chart] score ≤2; ≥3).

3.3.3 Informing the Participant's GP

The participant's General Practitioner (GP) will be notified, with the participant's consent.

4 TREATMENT

4.1 Trial treatment

4.1.1 Investigational Medicinal Product: Progesterone and Placebo

The Investigational Medicinal Product (IMP) is progesterone at a dose of 400 mg (i.e. two capsules of Utrogestan 200 mg®) to be taken vaginally twice daily from confirmation of an intrauterine gestation sac visible on ultrasonography, to 16 completed weeks of pregnancy or until miscarriage is confirmed. The up-to-date Investigator's Brochure for progesterone is available to all participating units.

The placebo will be a vaginal capsule, encapsulated in the same form as the IMP, and identical in colour, shape and weight.

4.1.2 Dose and Route of Administration

Dose

The ideal dose of progesterone to potentially prevent miscarriage is unknown. Our choice of 400 mg twice daily was made after a) a careful review of the existing literature, b) an extensive survey of UK clinicians, c) a review of clinical practice and d) a review of other related evidence. The SmPC and the British National Formulary suggest a dose up to 400 mg twice daily. Progesterone vaginal capsules are commonly used for luteal support in Assisted Conception at a treatment dose of 400 mg twice daily, with no specific concerns on safety raised on this dose. Moreover, the PROMISE trial (HTA o8/38/o1), that has already randomised over 810 women to 400 mg of progesterone or placebo twice daily, has not identified any acceptability or adverse effect issues. Hence we consider the dosage of 400 mg twice daily of vaginal progesterone to be the optimal choice in order to ensure a clinically effective dose, and to minimise the risk of a negative trial result from therapy with a suboptimal dose.

Route

An immuno-modulatory effect of progesterone within the uterus is the key presumed mechanism for preventing miscarriage. The vaginal route is therefore rational since it delivers a greater proportion of the drug to the uterus. Furthermore, existing miscarriage studies and preterm birth studies have shown effectiveness when given via the vaginal route. For instance, 14 of 36 studies of second/third trimester progesterone to prevent preterm birth (identified by a recent systematic review) used vaginal progesterone, with significant improvements being observed for various clinical outcomes, confirming the biological effects of vaginal progesterone²¹. Finally, a survey of women has found very high acceptability for the vaginal route.

Two vaginal capsules must be inserted vaginally (or rectally if preferred by the participant) twice daily. The first dose should be taken the evening following randomisation and subsequently every morning and evening until 16 completed weeks of pregnancy or until miscarriage is confirmed.

ISRCTN: 14163439

4.1.3 Packaging, Formulation and Supply

Investigational medicinal products will be procured, assembled, packed and quality assured by Besins Healthcare, a global clinical services company with whom we have worked in previous clinical trials. Besins Healthcare holds a Manufacturers' Licence for tablets and capsules under the Good Manufacturing Practice requirements (EU Directive 2003/94/EC) and in compliance with Good Clinical Practice (GCP; Clinical Trials Directive 2001/20/EC) Annex 13 requirements. Besins Healthcare will over-encapsulate the IMP and placebo and dispense into containers accordingly.

At study initiation, the Trial Office will arrange an initial supply of progesterone and placebo to be delivered by Besins Healthcare to the pharmacist of each study site. Local pharmacists will check the amount and condition of the supply, and confirm these details in a Proof of Receipt form.

The SmPC for progesterone states that progesterone should be stored below 25°C in a dry place. Shipments from Besins Healthcare will be temperature-monitored. Participants will be advised to keep their trial treatment packs away from extremes of temperature and out of the reach of children.

All the details of trial drug supply, labelling, storage and preparation will be as per the requirements of the Medicines for Human Use (Clinical Trials) Regulations 2004. Besins Healthcare will provide the Qualified Person for release of trial drug (QP) batch release service under the requirements of the Medicines for Human Use (Clinical Trials) Regulations 2004.

4.1.4 Dispensing and Accountability

At randomisation, the trial treatment number will be provided and this reference will correspond to a trial treatment pack available in the local hospital pharmacy. The pharmacist will receive notification of the name and trial number of the randomised woman and will prepare the trial treatment pack for dispensing. The trial treatment pack will contain between five and 12 weeks' supply, as appropriate to the duration from gestation at presentation until 16 weeks of gestation, for use by each participant.

The local pharmacist should keep accurate records of trial drugs dispensed using a pharmacy log provided by the PRISM Trial Office. Trial drugs must be kept in the packaging supplied and under no circumstances used for other participants or non-participants.

4.1.5 Treatment Duration

The treatment period will be determined by the gestational age at randomisation, ranging from five weeks (for women presenting at 12 weeks of gestation) to 12 weeks (for women presenting at five weeks of gestation). Trial treatment will be stopped at 16 weeks of gestation or if a miscarriage occurs.

4.1.6 Resupply to Centres

The computer program underpinning the randomisation process will automatically notify Besins Healthcare when a local study centre supply is low, to enable the IMP provider to issue another batch of trial drugs to the pharmacy. However, if the local pharmacist notices that supplies are becoming depleted and additional supplies could be needed, the site should contact the PRISM Trial Office, who will be able to initiate an additional supply.

4.2 Compliance Monitoring

The dispensing of the PRISM trial drug will be recorded in the pharmacy drug accountability log. The Trial Coordinator will periodically monitor the trial drug chart to verify that the dispensing system is being followed, to note any deviations from the quarterly schedule, and notify local PIs of any problems or deviations.

Participants will be asked to return completed, partially used and unused treatment packs to the trial centres. The research nurse at each local centre will receive the empty/partially used/unused treatment packs, and record the information for each trial participant, in the database. In an effort to improve compliance, women who fail to return the treatment packs, whether empty or not, will be contacted by telephone or email by the research nurse

ISRCTN: 14163439

for advice and support. Non-compliance is defined as less than 80% usage of the appropriate number of vaginal capsules for the gestational age at randomisation.

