5.2.4 Trial Steering Committee (TSC)

- To provide independent supervision of the scientific and ethical conduct of the trial on behalf of the Trial Sponsor and funding bodies.
- To review data, participant compliance, completion rates, adverse events (during treatment and up to end of follow-up).
- To receive and consider any recommendations from the DMC on protocol modifications.

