6.2 Secondary Outcome Measures

- Gestation at delivery.
- · Ongoing pregnancy at 12 weeks (range 11 to 13 weeks) of gestation.
- · Miscarriage rate (delivery before 24 weeks of gestation).
- Survival at 28 days of neonatal life.
- Chromosomal and congenital abnormalities.
- · Adverse events.
- · Antenatal complications (such as pre-eclampsia, growth restriction).
- If delivery ≥24 weeks, mode of delivery, birth weight, arterial and venous cord pH, APGAR scores, and resuscitation data.
- Neonatal outcomes: ventilation support and neonatal complications (such as infection, retinopathy of prematurity, necrotising enterocolitis and intraventricular haemorrhage).

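### The compliance definition in section 4.2 uses the full planned course as denominator, so a fully adherent woman who miscarries before about 14 to 16 weeks is classed as non-compliant

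*Protocol*

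**What the plan says.** Section 4.2 sets the rule: "Non-compliance is defined as less than 80% usage of the appropriate number of vaginal capsules for the gestational age at randomisation". What that number is follows from sections 4.1.4 and 4.1.5. Section 4.1.5 says: "The treatment period will be determined by the gestational age at randomisation", with a course "ranging from five weeks (for women presenting at 12 weeks of gestation) to 12 weeks (for women presenting at five weeks of gestation"). Section 4.1.4 sizes the pack in the same way, as five to 12 weeks' supply running to 16 weeks of gestation.

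Section 4.1.5 then gives the stopping rule: "Trial treatment will be stopped at 16 weeks of gestation or if a miscarriage occurs". Sections 4.1.1 and 4.1.2 also end dosing at 16 completed weeks or when miscarriage is confirmed. No section shortens the compliance denominator for a woman whose treatment ends this way, or exempts her from the definition.

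Compliance is meant to be looked at: section 5.2.4 lists among the tasks of the Trial Steering Committee (TSC) "To review data, participant compliance, completion rates, adverse events (during treatment and up to end of follow-up").

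**The concern.** The denominator depends only on gestational age at randomisation, while the numerator is cut off by an event that the trial hopes to prevent. A woman who inserts every capsule until the protocol tells her to stop is still counted as non-compliant if the stop comes early enough.

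Two things follow. First, the compliance rate mixes failure to use the capsules with early pregnancy loss and cannot separate them. If the trial finds no effect, readers will want to know whether women took the drug, and this measure cannot tell them. Section 4.1.2 shows that the question matters to the investigators, since the dose was chosen partly to avoid a negative result from inadequate therapy. Second, the label depends on outcome. If progesterone reduces early loss, the progesterone arm will look more compliant than placebo with identical behaviour, and any summary restricted to compliant women would drop most early losses.

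**Working it through.** **Inputs from the protocol.** Two capsules twice daily (section 4.1.2), so 4 a day and 28 a week. Planned course of 5 weeks for entry at 12 weeks and 12 weeks for entry at 5 weeks (section 4.1.5). Threshold of 80% (section 4.2). Arm size 2075 (section 7.1).

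**The plan's own course lengths.** 17 − 12 = 5 and 17 − 5 = 12, so section 4.1.5 corresponds to a course of 17 minus entry week. Counting strictly to 16 weeks and 0 days gives 16 minus entry week (4 to 11 weeks). Both are carried through below.

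**When a fully adherent woman reaches 80%.** Capsules planned = 28 × planned weeks. Gestation at 80% = entry + 0.8 × planned weeks.

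| Entry (weeks) | Planned weeks (17 − entry) | Capsules | 80% of capsules | Weeks needed | Gestation at 80% | Same, if course is 16 − entry |
|---|---|---|---|---|---|---|
| 5 | 12 | 336 | 268.8 | 9.6 | 14.6 | 13.8 |
| 8 | 9 | 252 | 201.6 | 7.2 | 15.2 | 14.4 |
| 10 | 7 | 196 | 156.8 | 5.6 | 15.6 | 14.8 |
| 12 | 5 | 140 | 112.0 | 4.0 | 16.0 | 15.2 |

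On either count the threshold lies between about 14 and 16 weeks' gestation.

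**Highest possible usage for a woman who miscarries** = (gestation at loss − entry) ÷ planned weeks:

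- entry 8, loss at 10: 2/9 = 22% (2/8 = 25% on the shorter count)
- entry 5, loss at 8: 3/12 = 25%
- entry 8, loss at 12: 4/9 = 44%
- entry 12, loss at 14: 2/5 = 40%

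**Share of an arm affected.** The protocol gives neither the rate nor the timing of loss before 16 weeks, so these are assumptions: entry week g uniform from 5 to 12; time from randomisation to loss exponential with mean m = 2, 3 or 4 weeks, restricted to losses before 16 weeks; 25-35% of the arm lost before 16 weeks. With planned course C, the share of these women below 80% is the average over g of 1 − exp(−0.8C/m), divided by the average over g of 1 − exp(−(16 − g)/m).

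| m (weeks) | C = 16 − g | C = 17 − g |
|---|---|---|
| 2 | 0.969 | 0.992 |
| 3 | 0.940 | 0.981 |
| 4 | 0.918 | 0.971 |

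- Lowest: 0.918 × 25% = 23.0% of the arm, about 476 of 2075.
- Highest: 0.992 × 35% = 34.7% of the arm, about 720 of 2075.

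Restriction to losses before 16 weeks brings the mean time to loss down to about 1.8 to 2.6 weeks, so this model places losses early. As a check against later timing, suppose losses are spread evenly from entry to 16 weeks. The share below 80% is then 80% with C = 16 − g, and between 0.8 × 12/11 = 87% (entry at 5) and 0.8 × 5/4 = 100% (entry at 12) with C = 17 − g. The lower end for the arm becomes 0.80 × 25% = 20%.

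**Difference between arms.** If progesterone lowered losses before 16 weeks by 5 percentage points (an assumption), apparent non-compliance would differ by 5 × 0.918 = 4.6 to 5 × 0.992 = 5.0 points with identical capsule use (4.0 points at the 80% share).

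**The case against.** The strongest reply is that nothing in the protocol analyses this label. Section 7.3 specifies intention to treat, with data sought on all women whatever their compliance. Sections 7.3.2 to 7.3.5 contain no adherent-only or compliance-adjusted analysis, and the sample size in section 7.1 has no compliance term. This stands. A reader might infer that the primary result is biased; the documents do not support that. A statistical analysis plan, which is not at hand, could also define its own denominator for any adherence analysis.

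A second reply is that section 5.2.4 does not say the TSC will see this binary label, or see it by arm. Section 5.1.6 has the TSC view safety data blinded, and section 8.4 keeps it unaware of interim results. This also stands: an arm difference is unlikely to reach the TSC during the trial, though a distorted overall rate could.

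A third reply is that the word appropriate in section 4.2 leaves room for an early stop. The sentence ties the number to gestational age at randomisation, when no later loss can be known, so this reading is weak. If it is what was meant, one clause would say so.

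Two further inferences go too far. One is that every woman who miscarries is misclassified. Section 6.2 defines the outcome as "Miscarriage rate (delivery before 24 weeks of gestation"), and losses after the 80% point are not affected. The other is that the label nearly duplicates the outcome. The primary outcome is live birth beyond 34 weeks, and the label also picks up genuine non-use while missing later losses, stillbirths and births before 34 weeks.

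**Conclusion.** The point holds in a limited form. Section 4.2 states a rule that conflicts with the protocol's own stopping rule and gives a wrong compliance figure for women who miscarry before about 14 to 16 weeks. That threshold comes from the protocol's figures alone. The share of an arm affected, roughly 23-35% (20% at the lower end if losses are spread evenly to 16 weeks), rests on the assumed loss rate and timing. The between-arm difference also needs a real effect of progesterone on early loss.

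The damage is confined to the compliance measure and to any later adherence-based summary. The correction is worth making because compliance is defined, recorded and listed for review, and because it costs little.

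**What to change.** Reconcile section 4.2 with the existing stopping rule in one sentence: the denominator is the number of capsules due from the first scheduled dose to the earlier of 16 completed weeks or confirmed miscarriage, and non-compliance is use of less than 80% of that number. A woman who takes every dose until miscarriage then scores 100%. Use this definition in compliance reports and in any adherence summary.

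Do not shorten the denominator for other early stops. Section 4.4 treats withdrawal of treatment on medical grounds as premature cessation, and counting those women as compliant would hide real under-exposure. No treatment rule changes.

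The cost is one sentence and a small check of the data forms. Capsule returns (section 4.2) and miscarriage (section 6.5.2, Table 2) are already recorded. The first scheduled dose follows from the randomisation date (section 4.1.2). The protocol does not explicitly list the date on which miscarriage was confirmed, so the form should capture it if it does not already.

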4.3 Excluded Medications or Interactions

Progesterone may interfere with the effects of bromocriptine and could raise the plasma concentration of ciclosporin. The metabolism of progesterone is accelerated by rifamycin, an antibacterial agent. Ketoconazole may increase the bioavailability of progesterone.

With participants' consent, the GPs of all the women recruited to the PRISM study will be informed of their participation. Moreover, all the participants will be given a small information card with contact details of the local PRISM investigator (a sample card is available separately), to carry these particulars for the purpose of directing clinicians to information regarding potential drug interactions. Concomitant therapy will be at the discretion of the care-providing clinicians.

Other than the above drugs and other progestogen preparations, the initiation of treatment for another indication will not necessitate withdrawal from the PRISM study.

4.4 Withdrawal of Treatment

A participant may be withdrawn from trial treatment if it becomes medically necessary in the opinion of the investigator(s) or clinician(s) providing patient care. In the event of such premature treatment cessation, PRISM study personnel will make every effort to obtain and record information about the reasons for discontinuation and any adverse events, and to follow up all safety and efficacy outcomes as appropriate.

A participant may voluntarily decide to cease taking the PRISM study treatment at any time. If a participant does not return for a scheduled visit, attempts will be made to contact her and (where possible) to review compliance and adverse events. If a woman decides after randomisation that she does not wish to continue her pregnancy, she may withdraw herself from the trial. We will aim to document the reason(s) for self-withdrawal.

Clear distinction will be made between withdrawals from trial treatments whilst allowing further follow-up, and any participants who refuse any follow-up. If a participant explicitly withdraws consent to any further data recording then this decision will be respected and recorded on the electronic data capture system. All communications surrounding the withdrawal will be noted in the participant's records and no further data will be collected for the participant.

4.4.1 Unblinding

Participants, investigators, research midwives/nurses and other attending clinicians will remain blind to the trial drug allocation throughout the duration of the trial.

Should any Serious Adverse Event occur, the management and care of the participant will be initiated as though the woman is taking progesterone. Cases that are considered serious, unexpected and possibly, probably or definitely related (please refer to section 5.1) will be unblinded only at the Trial Office by the PRISM Trial Coordinator, for reporting purposes. The attending clinician and local PI will not be made aware of the actual trial drug.

In all other circumstances, investigators and research midwives/nurses will remain blind to drug allocation whilst the participant remains in the trial. However, if a participant is withdrawn from the trial and only if the drug allocation is required for the continued medical management of the withdrawn participant, clinicians should contact the PRISM Trial Office or use the online PRISM code-break system. This service will be available 24 hours a day, seven days a week.

5 SAFETY MONITORING PROCEDURES

A recent review showed no clear or consistent evidence of serious adverse effects on the mother or the baby as a result of progesterone treatment during pregnancy (please refer to section 2.1.1). There is moreover substantial

ISRCTN: 14163439

evidence to indicate that progestogen supplementation is safe to the mother and the fetus (at the proposed dose for the PRISM trial of 400 mg twice daily)⁹⁻¹¹. The unknown risk of fetal abnormalities should be weighed against the risk of miscarriage.

There may yet be unexpected serious adverse reactions associated with progesterone when used in pregnant women. Progesterone has been prescribed to pregnant women in the PROMISE trial, to evaluate its effectiveness in preventing miscarriage. The Investigator's Brochure lists some rare but serious adverse reactions (available separately).

The Medicines for Human Use (Clinical Trials) Regulations 2004 define categories of adverse events, the responsibilities of the investigators to notify adverse events to the Trial Sponsor and the responsibilities of the Trial Sponsor to report to the regulatory authority and ethics committee. It will therefore be imperative for all investigators to maintain a thorough understanding of anticipated adverse events and the process for reporting such events.

5.1 General Definitions

5.1.1 Adverse Events (AEs)

An AE is:

- Any unintentional, unfavourable clinical sign or symptom, including complications of miscarriages (but not miscarriage itself).
- · Any new illness or disease or the deterioration of existing disease or illness.
- · Any clinically significant deterioration in any laboratory assessments or clinical tests.

The following are not AEs:

- Miscarriage or intrauterine death.
- A pre-existing condition (unless it worsens significantly during treatment).
- · Diagnostic and therapeutic procedures likely in a normal pregnancy, such as ultrasound.

